10.2 PATHOLOGY/CORRELATIVE/SPECIAL STUDIES

Tumor Collection and Screening

10.2.1 Pre-treatment diagnosis confirmation:

All patients will have histological or cytological confirmation of a diagnosis at their treating institution prior to treatment. If necessary a patient may have to undergo a biopsy of their disease as per standard clinical practice to ensure that a proper diagnosis of their disease is made. Tissue will be obtained for correlative studies only after a definitive diagnosis has been made by pathology and informed consent has been obtained.

10.2.2 Biopsy specimen collection for correlative studies:

Following informed consent, the first 20 patients enrolled on the phase II portion will undergo mandatory research biopsies. All biopsies will be performed at MSKCC or other participating institutions. These patients will undergo a pre-treatment biopsy and then a post-treatment biopsy (C1D8) that will be performed after week 1 of the combination therapy. Biopsies at the time of progression will be optional but encouraged. After 20 paired biopsy specimens are obtained, the remainder are optional and encouraged if additional funding is identified. If an open incisional biopsy is performed, 1 cm³ of tissue will be flash frozen and 0.5 to 1cm³ will be formalin fixed and sent to pathology for correlative studies. Alternatively, a CT guided core biopsy could be performed. Core biopsy will be performed of a lesion of at least 2 cm by a study interventional radiologist with local anesthesia and through a single entrance site on the skin surface, up to five tissue cores of the GIST will be obtained. Four cores will be flash frozen and one core will be fixed in formalin for correlative pathology. We believe that both approaches will provide sufficient tissue to do the proposed studies. As mentioned in 10.2.1, we may also collect tissue from patients required to undergo a pre-treatment biopsy for confirmation of diagnosis. A patient may be excused from this requirement if tissue is not deemed accessible or for safety reasons as determined by local study investigator. In such a case, subsequent patients will be approached for a mandatory biopsy until a total of 20 paired patient biopsies are obtained. Biopsies will not be performed on the Phase I portion of the protocol.

10.2.3 Research Blood:

Research blood will be drawn on the Phase Ib portion at the time points noted in Tables 10.A and 10.B for BJJ398 and imatinib plasma levels. Research blood will be obtained on the Phase II portion at baseline, 2 weeks after single agent imatinib lead in (+/-3 days) prior to Cycle 1 Day 1, and at C1D15 and C2D1 after the combination therapy started from all patients. All blood samples should be obtained prior to the daily dose of imatinib +/- BJJ398; i.e. a trough level. Research blood will be used to evaluate the steady-state imatinib trough level.

10.2.4 Collection of Specimen(s):

Tumor samples will be collected pre-treatment from the first 20 patients enrolled on the Phase II portion of the trial who have accessible tumor for biopsy and will start imatinib de novo for this trial. Also, tissue will be collected from any subsequent patients who require standard of care biopsies prior to systemic treatment, or those patients who volunteer for research biopsies if funding is available.

MEMORIAL SLOAN-KETTERING CANCER CENTER
IRB PROTOCOL

IRB#: 14-140 A (7)

10.2.4 Handling of Specimens(s):

For each sample indicate the unique patient study identification number, histology diagnosis, and the date of the specimen.

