After consent, and prior to treatment, the first 20 patients enrolled on the Phase II portion of the study across all sites will have a dedicated open incisional or core biopsy of their disease. All biopsies will be performed at MSKCC or other participating institutions. Biopsies on subsequent patients will not be mandated, but encouraged if additional funding is identified. A patient may be excused from this biopsy requirement if tissue is not accessible or if investigator determines that the patient should not undergo this biopsy. If this occurs, a biopsy will be mandated in additional patients to ensure that at least 20 participants undergo a biopsy. Upon initiation of treatment, patients who underwent a pre-treatment biopsy will undergo a second biopsy after one week (C1D8) of combination of BGJ398 and imatinib treatment and at time of disease progression. All patients will undergo baseline staging FDG PET and body imaging and repeat FDG PET scans during week three of the combination therapy of treatment (C1D21) as part of standard of care. Four weeks of treatment (28 days) will be considered one cycle. Imaging with standard CT scans and response evaluations will occur every 8 weeks for the first 32 weeks regardless of treatment interruption and then on Day 1 of every 3rd cycle thereafter.

All participants on the Phase II portion will have a 2-week lead in of imatinib. Blood will be drawn at the end of this period to establish steady-state imatinib serum trough levels. After blood for imatinib levels are obtained, BGJ398 at the established Phase II dose and treatment schedule will be added to the regimen. The start of the combination therapy will mark the beginning of cycle 1 (Day 1 cycle 1). The initiation of BGJ398 will not be contingent on the imatinib level; rather, BGJ398 can be started after the blood draw from imatinib levels is performed. Blood will be drawn again approximately 3-5-weeks after the initiation of the combination therapy to establish the steady-state imatinib serum trough levels in the presence of BGJ398.

9.1 Dose Rationale:

Phase Ib: The primary endpoint of the phase 1b portion of this study is to determine the maximum tolerated dose (MTD) and the Recommended Phase 2 Dose (RP2D) and treatment schedule of BGJ398 administered in combination with imatinib in patients with GIST. The phase Ib will be pursued in standard 3+3 format, based on toxicities encountered during the first cycle of therapy.

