12.1.2 Disease Parameters

Measurable disease. Measurable lesions are defined as those that can be accurately measured in at least one dimension (longest diameter to be recorded for non-nodal lesions and short axis for nodal lesions) as >20 mm by chest x-ray, as >10 mm with CT scan or MRI, or >10 mm with calipers by clinical exam. All tumor measurements must be recorded in millimeters (or decimal fractions of centimeters).

Non-measurable disease. All other lesions (or sites of disease), including small lesions (longest diameter <10 mm or pathological lymph nodes with ≥ 10 to <15 mm short axis), are considered non-measurable disease. Bone lesions, leptomeningeal disease, ascites, pleural/pericardial effusions,

MEMORIAL SLOAN-KETTERING CANCER CENTER
IRB PROTOCOL

IRB#: 14-140 A (7)

lymphangitis cutis/pulmonitis, inflammatory breast disease, and abdominal masses (not followed by CT or MRI), are considered as non-measurable.

Target lesions. All measurable lesions up to a maximum of 2 lesions per organ and 5 lesions in total, representative of all involved organs, should be identified as target lesions and recorded and measured at baseline. Target lesions should be selected on the basis of their size (lesions with the longest diameter), be representative of all involved organs, but in addition should be those that lend themselves to reproducible repeated measurements. It may be the case that, on occasion, the largest lesion does not lend itself to reproducible measurement in which circumstance the next largest lesion which can be measured reproducibly should be selected. A sum of the diameters (longest for non-nodal lesions, short axis for nodal lesions) for all target lesions will be calculated and reported as the baseline sum diameters. If lymph nodes are to be included in the sum, then only the short axis is added into the sum. The baseline sum diameters will be used as reference to further characterize any objective tumor regression in the measurable dimension of the disease.

Non-target lesions. All other lesions (or sites of disease) including any measurable lesions over and above the 5 target lesions should be identified as non-target lesions and should also be recorded at baseline. Measurements of these lesions are not required, but the presence, absence, or in rare cases unequivocal progression of each should be noted throughout follow-up.

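### Nothing keeps a research-biopsied lesion out of the RECIST and Choi target sum, so an open biopsy of a small sole target lesion could be read as shrinkage

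*Combined protocol and SAP*

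**What the plan says.** **Who is biopsied, and when.** Section 10.2.2 says that "the first 20 patients enrolled on the phase II portion will undergo mandatory research biopsies" and that "These patients will undergo a pre-treatment biopsy and then a post-treatment biopsy (C1D8) that will be performed after week 1 of the combination therapy". Patients may be excused for access or safety reasons, and others are then approached until 20 pairs exist.

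**Method and volume.** Section 9.0 allows either technique: each of these patients "will have a dedicated open incisional or core biopsy of their disease". For the open technique, section 10.2.2 gives the volumes: "If an open incisional biopsy is performed, 1 cm³ of tissue will be flash frozen and 0.5 to 1cm³ will be formalin fixed". A minimum lesion size is stated for the other technique only: "Core biopsy will be performed of a lesion of at least 2 cm by a study interventional radiologist".

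**Which lesion.** Section 8.0 refers to section 9.1 for how biopsies are selected. Section 9.1 is the dose rationale and has no rule for choosing a lesion; the text of 9.0 before it says which patients are biopsied, not which lesion.

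**Target lesions.** Section 12.1.2 takes all measurable lesions up to two per organ and five in total. It adds: "Target lesions should be selected on the basis of their size (lesions with the longest diameter"), subject to their being reproducibly measurable. Biopsied lesions are not mentioned.

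**Timing.** Section 10.1.2 places baseline imaging and the surgical biopsy in the same window of up to 4 weeks before therapy, in no stated order. The first response CT is at C3D1 (Table 11, note f).

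**Response.** A RECIST partial response is a fall of at least 30% in the target sum from baseline (12.1.4.1). A Choi partial response needs a fall in size of at least 10%, or a fall in density of at least 15% (Table 17).

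**The concern.** The primary endpoint is a diameter-based response in a single arm, judged against a fixed count. No control group would carry the same procedural artefact and cancel it. Tissue that a surgeon removes from a target lesion after the baseline CT is indistinguishable, under the response rules, from tissue lost to treatment.

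The pre-treatment biopsy may fall on either side of the baseline CT. The C1D8 biopsy cannot: it always comes after that scan and before the first response CT, even with the visit windows of 4 days for biopsies and 7 days for scans. In a patient with few lesions, the accessible lesion will often be in the target set, because section 12.1.2 takes every measurable lesion up to its caps.

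Two existing provisions do not deal with this. Confirmation after at least 4 weeks (12.1.9) does not help, because removed tissue stays removed. Review by the response committee (16.1.2) carries no instruction on biopsied lesions, and the plan does not ask for the biopsied lesion to be recorded.

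**Working it through.** **1. The plan's own design figures.** Inputs from section 14.0: N = 44, p0 = 0.45, p1 = 0.65, positive if more than 24 respond.

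- Type I error = P(X ≥ 25 | 44, 0.45) = 0.0775, which agrees with the stated 0.08.
- Power = P(X ≥ 25 | 44, 0.65) = 0.901, which agrees with the stated type II error of 0.1.

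**2. Volume per open biopsy** (10.2.2): 1 + 0.5 = 1.5 cm³ to 1 + 1 = 2 cm³.

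**3. Effect of one open biopsy on diameter.** Assumptions, neither of them in the documents: the lesion is a sphere that settles to a smaller sphere, and it is the only target lesion. Volume V = (π/6)d³; fractional loss of diameter = 1 − ((V − removed)/V)^(1/3).

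| Diameter | Volume | Loss, 1.5 cm³ removed | Loss, 2 cm³ removed |
|---|---|---|---|
| 2 cm | 4.19 cm³ | 13.7% | 19.5% |
| 2.5 cm | 8.18 cm³ | 6.5% | 8.9% |
| 3 cm | 14.14 cm³ | 3.7% | 5.0% |
| 4 cm | 33.51 cm³ | 1.5% | 2.0% |
| 5 cm | 65.45 cm³ | 0.8% | 1.0% |

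**4. Largest sole lesion at which one biopsy alone reaches a threshold t.** Solve V = removed/(1 − (1 − t)³).

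- Choi, t = 0.10: V = 1.5/0.271 = 5.54 cm³ or 2/0.271 = 7.38 cm³, so d = 2.19 to 2.42 cm.
- RECIST, t = 0.30: V = 1.5/0.657 = 2.28 cm³ or 2/0.657 = 3.04 cm³, so d = 1.63 to 1.80 cm.

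At 2 cm, therefore, one open biopsy passes the Choi size threshold but not the RECIST one. It does lower what treatment must achieve for a RECIST partial response. The remaining diameter must fall by 1 − 0.70/(1 − 0.137) = 18.9%, or 1 − 0.70/(1 − 0.195) = 13.1%, instead of 30%.

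**5. Dilution.** With one further, unchanged 4 cm target, the 2 cm lesion's loss becomes 0.137 × 2/6 = 4.6% to 0.195 × 2/6 = 6.5% of the sum, below both thresholds.

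**6. Illustration for the decision rule.** Let a share c of the non-responders among the 20 biopsied patients be counted as responders. At a true rate of 45% their response probability becomes 0.45 + 0.55c; the other 24 stay at 0.45. The type I error is the probability that the two counts together reach 25.

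| c (assumed) | Extra responders expected (20 × 0.55 × c) | Type I error |
|---|---|---|
| 0 | 0 | 0.078 |
| 1% | 0.11 | 0.083 |
| 2% | 0.22 | 0.088 |
| 5% | 0.55 | 0.105 |

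Nothing in the documents fixes c.

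**The case against.** The strongest reply is that the damaging case needs several conditions at once: an open biopsy, a small lesion, few or no other targets, and a patient who would not otherwise respond. The documents give no frequency for any of them. The sample-collection list in section 10.2 (items 2b and 2c) itemises both on-study collections as up to five cores, so open biopsy may be rare, and cores remove too little to matter. This stands, and 20 of 44 is an outer bound.

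Second, the bias need not run one way. An incision may not shorten the longest diameter, and swelling or bleeding could enlarge the lesion or change its density. A reader might infer that biopsy can only push towards response; the documents do not support that. They report intratumoral bleeding on imatinib (3.3.2) and early paradoxical enlargement of responding tumours (12.1.5). What remains is that tissue loss itself favours response; measurement error in either direction is still a reason to keep such lesions out of the sum.

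Third, partial safeguards exist. Section 12.1.2 lets a lesion that does not lend itself to reproducible measurement be passed over for the next largest, and section 12.1.3 asks for baseline evaluation as close to treatment as possible. Neither mentions biopsied lesions, so both leave the choice to each site.

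A reader might also go further and say that two open biopsies after the baseline CT manufacture a RECIST response in a 2 cm lesion. The arithmetic gives a 34 to 64% cut, but removing 3 to 4 cm³ from 4.19 cm³ takes 72 to 95% of the lesion. That is close to excision, not the incisional biopsy that the protocol describes.

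**Conclusion.** The gap is real and modest. The plan lets a lesion that undergoes an open research biopsy serve as a RECIST or Choi target, and one of the two biopsies always falls between the scans being compared. For a sole spherical target of about 2 to 2.5 cm, one open biopsy could cut diameter by about 7 to 20%. That can meet the Choi size threshold alone at about 2.2 to 2.4 cm or less, and can contribute to a RECIST partial response at 2 cm without producing it. At 3 cm the effect is 5% or less.

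The documents do not support a claim that the primary endpoint is materially biased. Lesion sizes, numbers of targets and the share of open biopsies are all unknown. The figures of 0.083 to 0.105 rest on assumed conversion of 1 to 5%. A reader might quote 0.131, which is P(X ≥ 24 | 44, 0.45), but that amounts to lowering the cut by one, as if every trial gained one false responder. Choi response is secondary, with a confidence interval and no decision rule. This is a cheap improvement to make, not a flaw that undermines the design.

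**What to change.** 1. In sections 10.2.2 and 12.1.2, state that a lesion chosen for research biopsy is recorded as non-target whenever another measurable lesion exists.
2. Record in the eCRF which lesion was biopsied and by which method, open or core.
3. Where the biopsied lesion is the only measurable one, take the baseline CT after the pre-treatment biopsy. This removes the first biopsy from the comparison but not the one at C1D8, and no later scan can separate that tissue loss from drug effect. So add to section 14.0 a sensitivity analysis of response that counts patients with an open-biopsied sole target lesion as non-responders.

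The cost is a sentence in each of two sections, a short addition to the analysis plan and two eCRF items. A few patients will have one fewer target lesion. N = 44 and the rule of more than 24 responses are unchanged.

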3.3.3 Pharmacokinetics of Imatinib mesylate

3.3.3.1 Pharmacokinetics of Imatinib in healthy subjects and patients with normal hepatic and renal function

The pharmacokinetics of Gleevec® have been evaluated in healthy subjects and in population pharmacokinetic studies in over 900 patients. Imatinib is well absorbed after oral administration with C_{max} achieved within 2-4 hours post-dose. Mean absolute bioavailability is 98%. Following oral administration in healthy volunteers, the elimination half-lives of imatinib and its major metabolite, the N-desmethyl derivative, were approximately 18 and 40 hours, respectively. Mean imatinib AUC increased proportionally with increasing dose in the range 25mg - 1000mg. There was no significant change in the pharmacokinetics of imatinib on repeated dosing, and accumulation is 1.5-3 fold at steady state when Gleevec® is dosed once daily. At clinically relevant concentrations of imatinib, binding to plasma proteins in *in vitro* experiments is approximately 89-96%, mostly to albumin.

A pharmacokinetic study following continuous once daily oral administration of imatinib has been performed in two GIST patients. The preliminary results showed that the PK profiles in GIST patients are similar to that observed in CML patients. Imatinib is rapidly absorbed and a C_{max} of 2.9 µg/ml was reached at steady state following a 400 mg daily dose. The terminal life was 13h and there was 1/5 fold drug accumulation after one month dosing. The AUC (0-24) values were 23,748 ng/h/ml at steady state after a 400 mg dosing, which is similar to those seen in CML patients.

The terminal half-life ($t_{1/2}$) averaged to 10 to 23 hours (18 hours for the parent and 40 hours for the major metabolite (see below)) and there was a 2-3 fold accumulation of drug at steady state. These data are compatible with a schedule of once daily administration. The increase in mean plasma AUC values was proportional to dose up to 750 mg/day. The mean plasma AUC (0-24) at steady state following a continuous once daily oral dose of 750 mg was 62,259 ng/h/ml.

A food effect study has shown no significant differences in absorption when imatinib was administered either with food or in the fasting state. Since this agent has potential to irritate gastric mucosa, it is therefore strongly recommended that the agent be taken with food to decrease risk of gastric irritation.

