5.1.3 Administration of Imatinib mesylate

Imatinib will be supplied by Novartis. Imatinib is available in 100 mg and 400 mg scored capsule. Preferentially and unless otherwise clinically indicated, 400mg capsule will be used. The investigator should instruct the patient to take the study drug exactly as prescribed (promote compliance) and to notify the Investigator of any deviations. Patients will be instructed to record their daily study drug administration in the patient diary provided to them. Imatinib will be dosed at 400 mg once a day by mouth. Because of the potential for intestinal irritation, the capsule should be taken during a meal and with a large glass of water (8 oz) to minimize the chance of irritating the esophageal and/or gastric mucosa. Patients should keep normal eating habits; however, low-fat (i.e. continental) breakfast is recommended avoiding xanthine (e.g. caffeine) or grapefruit containing food or beverages. Minimum of 1h should be allowed between last drug intake and going to bed. If vomiting occurs, no additional trial medication should be taken that day in an effort to replace the material that has been vomited. If a dose of imatinib is missed, the subject should take the dose as soon as possible, but only if there are 12 or more hours remaining before the next dose is due. If the next dose is due in less than 12 hours, the subject should skip the missed dose and take the next dose as scheduled. A study medication diary will be completed by the patients for each dose of Imatinib.

Instructions for dose modifications can be found in Section 9.

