5.2.3 Administration of BGJ398

BGJ398 will be taken orally, using treatment schedule A (once a day for 21 days on, 7 days off) or treatment schedule B (once daily for 7 days on, 21 days off) repeating in 28 day cycles. Patients should be instructed to take the daily dose of BGJ398 in the morning, at approximately the same time each day (24 ± 2 hour interval). Patients should consume a light breakfast each day (e.g., non-grapefruit-based juice, toast and jam). This should be followed by a 2 hour fast, after which the doses of study drug should be taken. Patients should continue to fast for 1 hour after the administration of study drug.

BGJ398 should be taken with a large glass of water (~250 mL) and consumed over as short a time as possible. Patients should be instructed to swallow the capsules whole and not chew them. If for any reason a breakfast was not consumed prior to taking the dose the patient should take the dose with a full glass of water, and continue to fast for an hour after taking the dose. If the patient forgets to take the scheduled dose in the morning, he/she should not take the dose more than 2 hours after the usual time and should continue treatment the next day. Any doses that are missed should be skipped altogether and should not be replaced or made up at the next scheduled dosing.

If vomiting occurs following the dosing of study drug, re-dosing is not permitted that same day. Dosing should resume the next day. BGJ398 is characterized by pH-dependent solubility, and therefore, medicinal products that alter the pH of the upper gastro-intestinal tract may alter the solubility of both compounds, and limit bioavailability. These agents include, but are not limited to, proton-pump inhibitors (e.g., omeprazole), H₂-antagonists (e.g., ranitidine) and antacids. Therefore, BGJ398 should be dosed at least 2 hours before or 10 hours after dosing with a gastric protection agent. Patients must avoid consuming Seville oranges or juice, grapefruit, grapefruit juice, grapefruit hybrids, or pummelos from 7 days prior to the first dose of study medication through the end of study participation. This is due to a potential CYP3A4 interaction with study medication. Normal oranges and orange juice are allowed.

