FFPE tumor tissue and pre-and post-treatment tumor frozen samples from the first 20 patients will be evaluated for inhibition of ETV1 and target pathway inhibition (MAP kinase, FGF, and KIT pathways). A variety of pathway markers of the MAP kinase and KIT pathways, including KIT, pKIT, pERK1/2, pAKT, PTEN, p-S6, p4E-BP1, pFRS2, FRS2, pPRAS40, pSTAT3 and STAT3 will be evaluated by IHC. ETV1 protein levels will also be evaluated by both western blot and immunofluorescence of frozen tissues, since there is no IHC grade ETV1 antibody.

1e. Pharmacodynamic studies by transcriptome

We will perform custom transcriptome analyses of the ETV1-dependent gene signature in GIST in pre- and post-treatment biopsies to assess the inhibition of the ETV1 transcriptional activity and correlate with response.

1f. Phenotypic changes in pre- and post-treatment tumors by IHC

In addition to the IHC of pKIT, pAKT, pERK1/2, etc as outlined in 1d in pre- and post-treatment biopsies, we will explore the relationship between the immunostains with the effects on tumor growth as assayed by the proliferation marker, Ki-67, and the apoptosis/cell death marker, cleaved caspase 3.

1g. Steady state plasma imatinib trough levels

The acute and steady state imatinib level will be assessed in all Phase Ib patients (one sample/timepoint). Patients enrolled onto treatment schedule A will have a plasma sample for imatinib levels drawn at C1D2 and C1D21 before imatinib is dosed on those days. Patients enrolled onto treatment schedule B will have a plasma sample for imatinib level drawn at C1D2, C1D7 and C1D21 before imatinib is dose on those days. The steady state imatinib trough levels will be obtained and evaluated in the two-week imatinib lead in phase (one sample/patient) and in the combination therapy phase (one sample/patient) from all patients in the Phase II portion of the trial. We will evaluate the effects of BGJ398 on imatinib steady state trough levels by comparing these two phases.

1i. BGJ398 pharmacokinetic assessment

BGJ398 levels will be assessed in all Phase Ib patients (1 sample per timepoint). Patients enrolled onto treatment schedule A will have plasma samples for BGJ398 levels collected at

MEMORIAL SLOAN-KETTERING CANCER CENTER
IRB PROTOCOL

IRB#: 14-140 A (7)

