Appendix B: Pill Diary for IRB #14-140: SCHEDULE A

Name: _____

MRN: _____

A phase Ib/II study of BGJ398 in combination with imatinib mesylate in patients with untreated advanced gastrointestinal stromal tumor (GIST)

	Total Daily Dose	Capsule Strength (mg)	Number of Capsule Given	Pill Bottles Returned?	Number of Capsule Returned
Imatinib				Y or N	
BGJ398				Y or N	

(Above to be Completed by RN)

PLEASE FILL OUT AND BRING THIS SHEET AT YOUR NEXT VISIT.

SPECIAL INSTRUCTIONS

- Imatinib should be taken orally with food. BGJ398 should be taken in the morning 2 hours after a light breakfast. No food should be consumed for 1 hour after taking the capsule. Both should be taken with a large glass of water (8oz).
- Do not chew or crush the capsule .
- Do not drink grapefruit juice or take herbal supplements such as St. John’s Wort while taking these medications.
- Take imatinib once a day, no less than twelve hours between each dose. If a dose of imatinib is missed, please take the dose as soon as possible, but **only** if there are **12 or more** hours remaining before the next dose.
 - a. If the dose is due in less than 12 hours, **skip** the missed dose and take the next dose as scheduled.
- Take BGJ398 once a day in the morning. If a dose of BGJ398 is missed, take as soon as possible **within 2 hours** of the missed dose. If 2 hours passes, **skip** the missed dose and take the next dose as scheduled.
- If vomiting occurs after taking either imatinib or BGJ398, even if it appears the whole capsule has been regurgitated, do not take a replacement dose. Resume at the next scheduled dose.
 - a. If consistent vomiting occurs please notify the study investigator

All missed doses should be recorded in this pill diary.

MEMORIAL SLOAN-KETTERING CANCER CENTER
IRB PROTOCOL

IRB#: 14-140 A (7)

DAY	MEDICATION	DATE	TIME	NUMBER of ___ mg capsules taken	NUMBER of ___ mg capsules taken
Example	Imatinib	01/01/2010	9:00 AM or PM	1	
	BGJ398		9:00 AM		1
Day 1	Imatinib				
	BGJ398				
Day 2	Imatinib				
	BGJ398				
Day 3	Imatinib				
	BGJ398				
Day 4	Imatinib				
	BGJ398				
Day 5	Imatinib				
	BGJ398				
Day 6	Imatinib				
	BGJ398				
Day 7	Imatinib				
	BGJ398				
Day 8	Imatinib				
	BGJ398				
Day 9	Imatinib				
	BGJ398				
Day 10	Imatinib				
	BGJ398				
Day	Imatinib				

MEMORIAL SLOAN-KETTERING CANCER CENTER
IRB PROTOCOL

IRB#: 14-140 A (7)

11	BGJ398				
Day 12	Imatinib				
	BGJ398				
Day 13	Imatinib				
	BGJ398				
Day 14	Imatinib				
	BGJ398				

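### In Phase II a sample drawn about 12 hours after an evening imatinib dose satisfies the protocol's trough rule and reads about 1.6 times the 24-hour level

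*Combined protocol and SAP*

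**What the plan says.** Section 10.2.3 (Research Blood) sets the Phase II sampling rule: "All blood samples should be obtained prior to the daily dose of imatinib", with or without BGJ398, and equates this with a trough. The draws are at week -2, at the end of the two-week imatinib lead-in, at C1D15 and at C2D1.

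For imatinib, section 5.1.3 says that "the capsule should be taken during a meal and with a large glass of water". Its only clock-related limit is "Minimum of 1h should be allowed between last drug intake and going to bed". A missed dose may be taken late, "but only if there are 12 or more hours remaining before the next dose is due". The diaries (Appendices B and C) instruct: "Take imatinib once a day, no less than twelve hours between each dose". Their example row offers 9:00 AM or PM for imatinib but 9:00 AM only for BGJ398.

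For BGJ398, section 5.2.3 requires a morning dose at a 24 ± 2 hour interval, after a light breakfast: "This should be followed by a 2 hour fast, after which the doses of study drug should be taken".

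The levels have three uses:
- Section 10.2.5, item 1g: "We will evaluate the effects of BGJ398 on imatinib steady state trough levels by comparing these two phases".
- Section 14.0: the ranges obtained are compared with published ranges and judged subtherapeutic, therapeutic or supra-therapeutic.
- Section 10.2.5, item 4: levels are split into quartiles and correlated with outcome.

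**The concern.** Drawing before that day's dose gives an end-of-interval sample only if the previous dose was about 24 hours earlier. The protocol secures that for BGJ398 with a morning rule and a ± 2 hour tolerance, but has no counterpart for imatinib. Because Phase II samples must precede BGJ398 as well, the draw on a BGJ398 dosing day is a morning draw. An evening imatinib taker then meets the rule at about half the dosing interval.

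Two kinds of analysis are exposed, in different ways. The range classes and quartiles use the absolute level, so pooling 12-hour and 24-hour samples sorts patients partly by when they take the drug. The lead-in versus combination comparison is within-patient, so a constant interval cancels and only a changed interval does harm. A longer interval in the lead-in than on the combination would look like the CYP3A4 inhibition that the comparison is meant to detect. The reverse would hide it.

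**Working it through.** The plan states no figure for this comparison, so there is nothing of its own to reproduce.

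**Inputs**, all from section 3.3.3.1. In healthy volunteers, "the elimination half-lives of imatinib and its major metabolite, the N-desmethyl derivative, were approximately 18 and 40 hours, respectively". The terminal half-life is also given as 13 h in two GIST patients and as a range of 10 to 23 h. Accumulation on once-daily dosing is given as 1.5 to 3 fold, and time to peak as 2 to 4 h.

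**Model.** One compartment, steady state, exponential decline after absorption. Check: accumulation = 1/(1 − 2^(−24/t½)) = 1.66 at 18 h, inside the stated 1.5 to 3 fold. (It is 1.23 at 10 h and 1.39 at 13 h, both below that band, and 1.94 at 23 h.) Adding first-order absorption with a peak at 2 to 4 h changes the ratios below by at most 0.002.

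**Step 1: regular evening dosing.** A 9 PM dose and a 9 AM draw are 12 h apart. Level relative to the 24 h trough = 2^(12/t½):

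| Half-life | 12 h / 24 h | 24 h / 12 h |
|---|---|---|
| 10 h | 2.30 | 0.44 |
| 13 h | 1.90 | 0.53 |
| 18 h | 1.59 | 0.63 |
| 23 h | 1.44 | 0.70 |

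**Step 2: a single late dose.** A morning taker who uses the missed-dose rule can also be drawn 12 h after a dose, but the previous interval was then 36 h. At 18 h, 2^(−12/18) = 0.630 and 2^(−24/18) = 0.397, and the usual trough is 0.397/(1 − 0.397) = 0.658 in single-dose units. The sample reads 1 + (0.630 − 0.397)/0.658 = 1.35 times the usual trough.

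**Step 3: the within-patient comparison.**
- Same interval at both draws: the timing ratio is 1.00.
- 24 h in the lead-in, 12 h on the combination: apparent rise of 59% at 18 h (44% to 130% over 23 to 10 h) with no interaction.
- 12 h, then 24 h: apparent fall of 37% (30% to 56%).
- A 4 h difference, such as an assumed move from breakfast to lunch: 2^(4/18) = 1.17.

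**Step 4: the group.** The documents give no share of patients whose interval changes, so the shares here are assumptions. If a share f changes by 12 h in one direction, the geometric mean ratio at 18 h is 1.587^f or 1.587^(−f):

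| Share f | 24 h then 12 h | 12 h then 24 h |
|---|---|---|
| 10% | 1.05 | 0.95 |
| 25% | 1.12 | 0.89 |
| 50% | 1.26 | 0.79 |

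Changes in opposite directions partly cancel.

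**Step 5: what a window would leave.** With an interval of, say, 22 to 26 h, the residual timing error at 18 h is at most 2^(2/18) = 1.08, or 2^(−2/18) = 0.93 on the other side.

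**The case against.** The strongest defence is that section 10.2.3 names a trough and a steady-state trough outright, so a competent site would draw at the end of the dosing interval. On that reading only a numeric tolerance is missing, and the AM or PM entry is an example row, not an instruction. This stands in part: intent is clear. But the condition actually written is met at 12 hours, section 5.1.3 does not exclude evening dosing, and section 14.0 describes no exclusion or adjustment by time since dose.

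Diaries do have date and time columns for each dose, so last-dose time is largely recoverable. That stands, and it makes the remedy cheaper. The visible Phase II lab instructions label samples with ID, date and study time point. Part of the Phase II sample form is not in the public copy, so it cannot be said that draw time goes unrecorded.

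A reader might infer that the BGJ398 fast forces patients to move imatinib once the combination starts. The documents do not support this: section 5.2.3 has patients eat a light breakfast before the fast, and imatinib fits with that meal. A change of timing is possible, not compelled.

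A reader might also infer that Phase Ib has the same lead-in artefact. It does not. Phase Ib has no imatinib-alone lead-in, the C1D2 draw is set at 24 h ± 60 min, and Table 10.A ties pre-dose draws to giving both drugs that day.

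Finally, the analysis is correlative. Section 14.0 says that it will not alter the combination dose, and it carries no decision rule. That limits the weight of the point.

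**Conclusion.** The point holds for Phase II. The rule as written admits samples from about 12 hours post-dose as troughs, and such a sample from a regular evening taker reads about 1.59 times the 24-hour level at an 18-hour half-life (1.44 to 2.30 over 23 to 10 h). The range classes and the quartile-outcome correlation are affected wherever morning and evening takers are pooled, whether or not anyone changes habit. The lead-in versus combination comparison is biased only by patients whose dose-to-draw interval differs between draws. Since no rate is given, the documents do not support a claim that the interaction estimate will be biased by any particular amount.

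The size rests on one-compartment decline and the protocol's own half-lives. The share of evening takers is unknown. This is a cheap improvement to a correlative analysis. It does not threaten the primary endpoint, the safety rules or the Phase II dose.

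**What to change.** In section 10.2.3, section 10.2.5 item 1g and section 14.0:

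1. Take the time of the last imatinib dose from the diary and pair it with the recorded draw time. Capture draw time if the Phase II form does not already do so.
2. Count a Phase II sample as a trough only if it was drawn within a pre-specified interval around 24 hours after that dose (22 to 26 h would serve as an example), with the same interval in the lead-in and on the combination.
3. Run the BGJ398-effect comparison, the therapeutic-range classes and the quartile analysis on qualifying samples, and list the others separately with their times.

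Separately, the dosing-time and meal statements in section 5.1.3, section 5.2.3, footnote a of Table 10.A (which has both drugs given together) and the Appendix B diary should be reconciled. No view is taken here on which is right.

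The cost is a sample-validity rule, at most one added form field, and the loss of some samples from the trough analyses.
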